6.1 Subject Recruitment, Consent and Enrollment

The investigator or designee should review all prospective subjects' medical histories to screen for eligibility.

6.1.1 Subject Recruitment

The investigator will provide patients who present to his practice with symptomatic knee pain and Radiographic evidence of OA in the tibio-femoral or patella-femoral compartment of the target knee (Kellgren-Lawrence Grades II- III), the opportunity to be considered as a candidate for this trial. Pre-procedure screening to confirm the diagnosis is not considered part of the study; however the informed consent form will advise the subject that their medical history records used to confirm diagnosis and X-rays will be incorporated into the study record. If all X-ray required for inclusion have not been done or present in medical records within 24 weeks of screening, they must be taken prior to randomization. These Xrays include:

- Weight bearing hip to ankle Anterior –Posterior (AP) of the involved knee (extremity)
- Standing AP of both knees in extension
- Standing Posterior-Anterior (PA) weight bearing of both knees at 45 degrees of flexion
- Supine lateral of the involved knee
- Sunrise view of both knees

6.1.3 Consent

The investigator will prepare an informed consent form (ICF) in accordance with this study protocol and all regulatory requirements (21 CFR Part 50) using the sample informed consent form provided by the sponsor. Changes to the ICF and amended ICF(s) must be approved by Arthrex's Clinical Research prior to submitting to IRB. A copy of the final IRB-approved ICF or amended ICF(s) must be maintained as part of the study file.

The subject candidate will be introduced to the study by the investigator. Interested patients will have the study thoroughly explained to them by the investigator and/or site coordinator. Additionally, informed consent forms will be provided to the patient so they may take home and review with significant others if desired. The informed consent process includes ensuring all of the patient's questions are answered. Once the subject decides if they want to participate in the clinical trial,

the site will obtain a signed consent from the subject and make arrangements to schedule them for Visit 2.

Prior to any study procedures, all subjects must document their consent for study participation and authorization for use and disclosure of health information by signing the IRB approved Informed Consent form.

6.1.4 Subject Status

Only those patients who meet the inclusion / exclusion criteria and who have signed the informed consent for the trial and proceeded to Visit 1 will have a status of "Screened". Subjects that are screened but do not meet inclusion/exclusion criteria will be considered, "Screen failed." Once the subjected is treated (has either randomized treatment) they will be considered "treated".

Subjects that are treated (has either randomized treatment) and do not complete the follow final visit will be considered "early termination". Subjects that complete Visit 8/12 months (365 days) will be considered complete.

Subjects receiving treatment, but not meeting all inclusion / exclusion are considered treated, and will be followed per the protocol but will be considered protocol deviations.

6.2 Study Visits

For this study all subjects will have a screening visit and three treatment visits to receive a series of intra-articular injections one week apart. Subjects will then return for follow-up visits at 2 months (60 days), 3 months (90 days), 6 months (180 days) and 12 months (365 days) post-treatment 1st injection.

6.2.1 Screening Visit 1 (-7 to -2 days)

Once the subject has signed the informed consent and prior to treatment, he/she will have the following data collected and procedures conducted:

- Medical history/Demographics
- Physical exam (Temperature, heart rate and blood pressure)
- Radiograph(s) (if not part of medical record) refer to section 6.1.1
- Urine pregnancy test (for females with childbearing potential)
- Concomitant Analgesics/Treatment review
- WOMAC survey (pain, stiffness, function)
- Inclusion/exclusion criteria review
- Kellgren-Lawrence grading
- Strokes Test Grading

• Inform subjects that they will return for visit 2 to receive their 1st IA injection and then to return at 1 week and 2 weeks for an additional IA injection. Additionally, inform that they will need to return for visits at 2, 3 and 6 months post-treatment 1st injection.

6.2.2 Treatment: Visit 2 (Day 0)

All subjects will have the following procedures at visits 2 prior to randomization:

- Concomitant Analgesics/Treatment review
- Inclusion /Exclusion review
- Whole Blood and ACP collected for analysis

6.2.2.1 Randomization

Once confirmed that the subject has met all the inclusion/exclusion criteria, the principal investigator will be permitted to proceed to randomization of the subject. An automated Internet-based randomization system will ensure concealed randomization of eligible consenting subjects. Subjects will be randomized to one of 2 treatment groups.

- **6.2.2.2** Investigational Arm: Three IA injections of 3-6 mL ACP at 1 week intervals. (n=60)
- **6.2.2.3** Control Arm: Three IA injections of 3-6 mL Normal Saline at 1 week intervals. (n=30)

Note: The volume of PRP produced during the ACP procedure differs per individual; therefore we are providing a range as noted in earlier justification. Additionally, the amount of Normal Saline will be determined by the volume of PRP produced during the ACP procedure, except the control subjects will receive only the same volume of Normal Saline as produced by their own blood during the ACP procedure.

6.2.2.4Venipuncture and Blood collection

Refer to Venipuncture and Blood Collection Procedure (Appendix 2-3)

6.2.2.5 Processing ACP

Refer to Venipuncture and Blood Collection Procedure (Appendix 2-3)

6.2.2.6 Blinding Procedure:

Subject blinding will be maintained by drawing blood from all subjects, then preparing and administering both treatments (ACP and Normal Saline) in a concealed, opaque syringe.

Blinding will be maintained by a separate clinician(s) designated to blind the syringes (i.e.: Laboratory Technician) from the staff designated to collect/assess patient outcomes and designated to administer the treatments (Investigator/ Sub-Investigator).

The subject, the evaluating physician, and coordinator will be blinded until 12 (365 days) months.

Refer to Blinding Procedure (Appendix 2-5)

6.2.2.7 IA Injection Procedure

Refer to Intra-articular Injection (Appendix 2-4)

6.2.2.8 Adverse event/device events

- Assess subjects during treatment for adverse events as defined in section 7.
- Assess for complications as defined in section 7.

6.2.2.9 Patient Management Plan

Instruct patient on the following:

- 1. He/she may experience transient pain, swelling, and/or effusion of the injected joint after IA injection.
- 2. Pronounced pain and extensive swelling should be reported to the physician.
- 3. He/she should avoid strenuous activities or prolonged weight-bearing for approximately 48 hours.
- 4. He/she should be able to resume baseline activities after 48 hours.

6.3 Study Visits

6.3.1 Treatment Visits

All subjects enrolled in the study will have the following procedures at visit 3 (1 week +/- 3 days) & visit 4 (2 weeks +/- 3 days):

- WOMAC survey (pain, stiffness, function)
- Concomitant Analgesics/Treatment review
- Adverse event assessment /device complications as defined in Section 7
- Venipuncture, processing, blinding and IA procedure.
- Refer to Visit 3 and 4 Venipuncture and Blood Collection Procedure (Appendix 2-3)
- Refer to Blinding Procedure (Appendix 2-5)

• Refer to Visit 2, 3 and 4 Intra-Articular Injection (Appendix 2-4)

6.3.2 Follow-Up Visit 5 [2 months (60 days)+/- 7 days], Visit 6 [3 months (90 days)+/- 7 days] & Visit 7 [6 months (180 days) +/- 14 days]

- WOMAC survey (pain, stiffness, function)
- Concomitant Analgesics/Treatment review
- Adverse event assessment

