7.3 Adverse Event and Unanticipated Adverse Device Effect Reporting

At every subject encounter, the investigator will determine if there has been an adverse event since the last encounter.

For this study, serious adverse events must be reported to Arthrex or designee within 24 hours of event discovery by the site and entered into the EDC database. At the time of the initial report, the outcome (resolution status) may not be known. Updated information must be entered into the EDC database until final resolution of the event.

UADEs must also be reported by the investigator to the approving IRB as soon as possible, but not later than 10 working days after the investigator first learns of the effect. The sponsor must report to the FDA, all reviewing IRBs, and participating investigators within 10 working days of notification from the investigator of a UADE.

The monitor will provide medical surveillance on adverse events and will evaluate all Serious Adverse Events (SAEs)

7.4 **Device Complications**

For this study all device malfunctions including ; unable to pull up outer syringe, unable to pull up inner syringe, damaged parts, cracked parts, packaging – device/component missing, packaging – broken in package, leaking, air mixed with blood, piece broke from device , frozen or other will be collected and reported on associated eCRF.

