8.7 Safety Endpoints

The primary safety endpoints for this study are based on adverse events. Details regarding analyses of adverse events are provided below. Briefly, adverse event endpoints will include, but are not limited to, the following patient specific endpoints:

- Any adverse event (per patient)
- Any treatment related AE
- Any serious AE
- Any serious AE that is treatment related
- Patient death

Specific endpoints such discomfort and pain, erythema, swelling, bruising, hemorrhage, and papules will be compared between treatment groups in terms of both per patient incidence rates and total counts. Fisher's exacts tests will be used to provide descriptive comparisons between incidence rates. Counts of AEs will be displayed overall and over time.

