8.8 Safety Analysis

Assessment of safety will be based primarily on the incidence and severity of complications and adverse reactions associated with the treatment. Adverse event rates will be summarized by type of AE and for specific AEs in two ways: 1) per patient using counts and percentages and 2) by event, summarizing event counts by visit interval over time. Treatment and procedure related events will be summarized by severity. Events listings will be provided that include details such as relatedness, severity, onset and resolution status will be provide for all events and for relevant subsets of events such as serious events and related events. All safety endpoints will be summarized separately for investigational and control groups. Incidence rates for grouped and individual adverse events will be compared using counts, percentages, and descriptive Fisher's exact test nominal p-values. Grouped adverse events will include events at least possibly related to study treatment and serious adverse events.

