8.9 Adverse events counts over time

The numbers of specific adverse events occurring pre-discharge and for each study interval will summarized separately for each relevant cohort. Counts of systemic adverse events will be summarized on a per patient basis. All other adverse events will be summarized on a per procedure basis.

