Appendix 2-1 Schedule of Events

	Screening	Т	reatment Vis	its		Follow	v —up Visits	
ACP IA FOR KNEE OA	Visit 1	Visit 2	Visit 3	Visit 4	Visit 5	Visit 6	Visit 7	Visit 8
	Day -2 to 07	Day 0	Week 1 +/- 3 days	Week 2 +/- 3 days	2 months +/- 7 days	3 months +/- 7 days	6 months +/- 14 days	EOS or 1year +/- 30 days
Informed Consent	X ¹							
History & Demographics	X ²							
Physical Exam (VS) • Knee Exam • Kellgren-Lawrence Grading • Strokes Test Grading	X ³							
Concomitant Medication/Therapy	X4	X 4	X ⁴	K 4	X4	X 4	X⁴	X4
WOMAC	X ⁵		X⁵	K₂	X ⁵	K₂	X₂	X ⁵
Enrollment Pregnancy (urine) Radiograph	X6	X 6						
Randomization		x						
Visit	X7	X 7	X 7	K 7	X 7	K 7	X 7	X ⁷
Treatment		X ⁸	X ⁸	K ⁸				
AE		X 9	X 9	Х ⁹	X ⁹	X 9	X9	X۹
Deviation	X ¹⁰	X ¹⁰	X ¹⁰	X ¹⁰	X ¹⁰	X ¹⁰	X ¹⁰	X ¹⁰
Completion								X ¹¹
Heme Profile		X ¹²						

Informed Consent process is conducted and the form is signed prior to any study related procedures.
 Medical & Surgical History and Demographics are collected at Screening
 Physical Exam (including Knee exam, Kellgren-Lawrence & Strokes Test) is done at screening
 Pain medication and therapy review are collected at screening and reviewed at each study visit
 WOMAC is completed at screening visit to confirm Inclusion Criteria # 4
 Available Inclusion/Exclusion Criteria is collected at screening and confirmed at V2 (Day 0) prior to randomization. Radiographs to confirm Inclusion #3 and exclusion #1 and 3. Radiographs are done prior to Randomization, if not complete and part of subject's medical historical medical record. Urine pregnancy is done at screening as when applicable.
 Visit Data collected all study Visits.
 Treatment form is collected at V2, V3 & V4.
 Adverse Events are collected at applicable at V2 thru V8.
 Deviations are collected at each V1 thru V8.
 Study Completion is done at Visit 8 or sooner if discontinues prior to Visit 8.

12. Whole blood and ACP collected for analysis.

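### After injection 3 no adverse-event contact is scheduled for 36-56 days (nominal 46, against 7 after injections 1 and 2), so mild local reactions to it depend on long recall

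*Combined protocol and SAP*

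**What the plan says.** Section 6.3.1 schedules treatment "procedures at visit 3 (1 week +/- 3 days) & visit 4 (2 weeks +/- 3 days". Injection 3 belongs to Visit 4. Section 6.3.2 then places the next contact at "Follow-Up Visit 5 [2 months (60 days)+/- 7 days", and Section 6.2 counts follow-up from the first injection. Section 6.2.2.2 gives the injection interval as 1 week.

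On collection of adverse events:

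- Section 7.3: "At every subject encounter, the investigator will determine if there has been an adverse event since the last encounter".
- Appendix 2-1, footnote 9: "Adverse Events are collected at applicable at V2 thru V8". The schedule has no column for a call, diary or visit between Visits 4 and 5.
- Appendix 2-6: the visit form for Visits 3 to 8 and unscheduled visits asks about events since the last visit.
- Appendix 2-4: the subject is watched for 10 minutes after each injection.
- Section 6.2.2.9: patients are warned of transient pain, swelling or effusion and told that "Pronounced pain and extensive swelling should be reported to the physician".

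On analysis:

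- Section 8.7 (Safety Endpoints): "Specific endpoints such discomfort and pain, erythema, swelling, bruising, hemorrhage, and papules will be compared between treatment groups", by per-patient incidence and by total count.
- Section 8.8 (Safety Analysis): adverse events are also summarized "by event, summarizing event counts by visit interval over time".
- Section 8.9, for non-systemic events: "All other adverse events will be summarized on a per procedure basis". The plan does not define a procedure.

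**The concern.** Local reactions to an intra-articular injection are expected soon after it. The plan asks about them roughly a week after injections 1 and 2, but not until about six and a half weeks after injection 3.

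Section 7.2 defines a mild event as transient, easily tolerated and needing neither medication nor medical evaluation. Such an event is unlikely to prompt a patient to call or come in, so after injection 3 it depends on what the patient remembers at Visit 5. Dating suffers as well, and Section 7.2 makes a strong temporal relationship part of both the possibly-related and the probably-related categories.

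Section 8.4.1 justifies 2:1 randomization by the wish to describe the safety profile of the investigational treatment more precisely. Less complete ascertainment after one third of the injections works against that aim. A lower count after injection 3 could mean better tolerance or poorer recall, and the data could not tell the two apart.

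**Working it through.** The plan states no figure for this gap, so there is none to reproduce. The check is visit-window arithmetic.

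**Inputs** (Sections 6.2, 6.3.1, 6.3.2 and Appendix 2-1)

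| Visit | Nominal day | Window |
|---|---|---|
| 2 (injection 1) | 0 | 0 |
| 3 (injection 2) | 7 | 4-10 |
| 4 (injection 3) | 14 | 11-17 |
| 5 (first follow-up) | 60 | 53-67 |

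**Time to the next scheduled adverse-event question.** Minimum = earliest next visit minus latest previous visit. Maximum = latest next visit minus earliest previous visit.

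| After | Nominal | Minimum | Maximum |
|---|---|---|---|
| Injection 1 | 7 - 0 = 7 | 4 - 0 = 4 | 10 - 0 = 10 |
| Injection 2 | 14 - 7 = 7 | 11 - 10 = 1 | 17 - 4 = 13 |
| Injection 3 | 60 - 14 = 46 | 53 - 17 = 36 | 67 - 11 = 56 |

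Like for like, the nominal ratio is 46/7 = 6.6. The ranges do not overlap: the shortest gap after injection 3 (36 days) exceeds the longest after either earlier injection (13 days).

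**Injections affected.** 90 of 90 x 3 = 270 planned: 60 of 180 ACP and 30 of 90 control.

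**Is the Day 0 anchor the cause?** No. Counting Visit 5 from injection 3 instead would make the gap 60 +/- 7 = 53-67 days. The cause is the missing contact.

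**Effect of a call.** A call 7 +/- 3 days after injection 3 falls between Day 11 + 4 = 15 and Day 17 + 10 = 27. The gap becomes 4-10 days, the same as after injection 1.

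**Secondary point: spacing of injections 2 and 3.** Both windows are tied to Day 0, so injections on Days 10 and 11 are within protocol. Of 7 x 7 = 49 permitted day pairs, the number with spacing d is 7 - |d - 7|:

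- d = 1, 2, 3: 1 + 2 + 3 = 6 pairs
- d = 11, 12, 13: 3 + 2 + 1 = 6 pairs
- d = 4 to 10: the other 37 pairs

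These are combinations of days, not expected frequencies.

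With Visit 4 set at 4-10 days after Visit 3, it falls on Days 4 + 4 = 8 to 10 + 10 = 20. Without a call, the gap to Visit 5 would then be 53 - 20 = 33 to 67 - 8 = 59 days, so re-anchoring alone does not help ascertainment.

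Keeping Days 11-17 as well is feasible. Visit 3 on Day 4 leaves Days 11-14, Visit 3 on Day 10 leaves Days 14-17, and dates between leave at least as many days.

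**The case against.** The arithmetic is not in dispute. The case on the other side concerns weight.

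- **No inferential harm.** The planned safety comparison is ACP against control, both blinded arms follow the same schedule, serious events go to the sponsor within 24 hours (Section 7.3), and the primary endpoint is untouched. This stands, and it limits the point to descriptive safety data.
- **Loss is assumed, not shown.** The documents contain no figure on recall. This also stands. The day counts are certain; the under-ascertainment is a risk of unknown size.
- **Per-patient incidence is partly protected.** A patient who also reacted to injection 1 or 2 is already captured. Only those whose sole reaction was mild, followed injection 3 and was then forgotten are missed. This stands for incidence, but total counts and counts by visit interval remain exposed.
- **Comparison across injections is not an objective.** The per-procedure wording in Section 8.9 sits beside terms such as pre-discharge that do not fit an injection series, so it may be carried-over text. This stands in part: the reading is uncertain, which is itself a reason to define the term. The gap in the absolute profile does not depend on it.
- **Other routes exist.** Patients may report by themselves, unscheduled visits carry the same question, and Visit 5 still asks. Self-report is requested for pronounced symptoms, and unscheduled visits are for matters needing immediate attention, so neither route is aimed at mild reactions.
- **Some mild knee pain is not an adverse event.** Section 7.1.1 excludes symptoms of the studied disease unless they are worse than expected or need intervention. This holds only partly, because Section 7.1.3 lists injection site pain, joint swelling and joint effusion as anticipated adverse events.
- **Injection spacing is a different topic.** That is fair. It is kept as a secondary point because the windows contradict the stated weekly interval and the correction is one sentence.

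**Conclusion.** The concern holds. No adverse-event contact is scheduled between injection 3 and Visit 5, a gap of 36-56 days (nominal 46), against 4-10 days after injection 1 and 1-13 days after injection 2 (nominal 7 each). It affects 90 of 270 planned injections.

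The consequence is a risk that mild, transient local reactions to the last injection are missed or poorly dated in both arms. That weakens the absolute reaction profile of the three-injection course and any comparison between injections. It does not show bias between arms and does not touch the primary endpoint or serious-event reporting.

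The conclusion rests on two assumptions: visits fall within their stated windows, and recall of mild events fades over several weeks. How many reactions would be lost cannot be computed from the documents. The point calls for an inexpensive improvement to the safety data.

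**What to change.** 1. **Add one contact.** In Section 6.3.2 and Appendix 2-1, schedule an adverse-event telephone call 7 +/- 3 days after injection 3, with the same questions as at Visits 3 and 4.
2. **Add one table and one definition.** In Sections 8.8 and 8.9, tabulate local adverse events by days since the most recent injection (0-7 days after injections 1, 2 and 3, then later) beside the counts by visit interval. Onset and treatment dates are already collected. State that a procedure means one injection.
3. **Secondary: re-anchor the treatment windows.** Define Visits 3 and 4 as 7 +/- 3 days after the preceding injection, so that consecutive injections are 4-10 days apart. If Visit 4 must also stay within Days 11-17, require both conditions. This does not replace the call.

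**Cost.** About 90 short calls by the existing blinded coordinators, a dated contact record for each, one schedule column, one safety table and one sentence on windows. The existing adverse-event form suffices, and no clinic visit or procedure is added. The change needs the usual sponsor, FDA and IRB approval (Section 9.16), and a missed call could count as a protocol deviation (Section 9.17). Sample size, efficacy endpoints and blinding are unaffected.

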6.3.3 Visit 8 (12 months (365 days) +/- 30 days)

- WOMAC survey (pain, stiffness, function)
- Concomitant Analgesics/Treatment review
- Adverse event assessments

7 Adverse Events

7.1 **Definitions**

7.1.1 Adverse Events

An adverse event (AE) is any undesirable experience (e.g., sign, symptom, illness, clinically significant abnormal laboratory value, or other medical event) occurring in a subject during the course of the study, whether or not it is related to the investigational treatment or procedure.

An AE does include a/an:

- Exacerbation of a pre-existing illness
- Increase in frequency or intensity of a pre-existing episodic event or condition
- Condition detected or diagnosed after study device use even though it may have been present prior to the start of the study treatment.
- Continuous persistent disease or symptoms present at baseline that worsen following the start of the study

An AE does not include a/an:

- Medical or surgical procedure (e.g., surgery, endoscopy, transfusion); the condition that leads to the procedure is considered an AE
- Pre-existing diseases or conditions present or detected at the start of the study that do not worsen
- Situations where an untoward medical occurrence has not occurred (e.g., hospitalizations for cosmetic elective surgery, social and/or convenience admissions)
- The disease or disorder being studied, or sign or symptom associated with the disease or disorder, unless the disease, sign or symptom is more severe than expected based on the subject's condition and/or requires intervention.

